### **5.3.3 Sensitivity Analyses for Primary Endpoint(s)**

To support the primary analyses, the following sensitivity analysis will be conducted:

- To test the sensitivity of the results to adjustment by the stratification factors, the primary analysis negative binomial model described above will be adjusted by the following additional covariates: sex, age (<40, ≥ 40).

### **5.3.4 Supplementary Analyses for Primary Endpoint(s)**

#### **5.3.4.1 Subgroup Analyses for Primary Endpoint(s)**

The generalizability of primary endpoint results when comparing fenebrutinib to placebo will be investigated by estimating the treatment effect in subgroups. If there are less than 5% subjects in one subgroup, the corresponding subgroup analysis will not be produced. Summaries of primary endpoint by these subgroups will be provided:

Stratification factor:

- Presence or absence of T1Gd+ lesions at screening

Key baseline demographics:

- Age (≥40 versus < 40)
- Sex (Female versus Male)
- Baseline EDSS (>4.0 versus ≤4.0)
- Region (North American versus other)

Disease characteristics:

- Prior disease modifying treatments within 6 months prior to randomization (yes or no)
- Prior steroid treatment within 3 months prior to randomization (yes or no)

### **5.3.4.2 Other Supplementary Analyses for Primary Endpoint(s)**

To investigate the treatment effect on different estimand attribute of analysis population, the primary analysis negative binomial model described above in Section 5.3.2 may be fitted on all randomized patients excluding subjects with major protocol deviation related to incorrect amount of fenebrutinib.

## **5.4 SECONDARY ENDPOINT(S) ANALYSIS(SES)**

### **5.4.1 Key/Confirmatory Secondary Endpoint(s)**

The secondary efficacy endpoints are:

- Total number of new or enlarging T2-weighted lesions observed on brain MRI at Weeks 4, 8, and 12.
- Proportion of participants free from any new gadolinium-enhancing T1 lesions and new or enlarging T2-weighted lesions observed on brain MRI at Weeks 4, 8, and 12.

#### **5.4.1.1 Total number of new or enlarging T2-weighted lesions**

Total number of new or enlarging T2-weighted lesions will be calculated as the sum of the individual number of new or enlarging lesions at Weeks 4, 8, 12. The estimands for the secondary endpoint of total number of new or enlarging T2 lesions, will follow the same hypothetical strategy and have the same attributes (except for variable) as for the primary endpoint. Number of new or enlarging T2 lesions and proportion of participants with new or enlarging T2 lesions at each scheduled visit will also be summarized by treatment groups.

#### **5.4.1.2 Proportion of Participants Free from any new Gadolinium-Enhancing T1 Lesions and new or Enlarging T2-Weighted Lesions**

The secondary endpoint of proportion of participants free from any new gadolinium-enhancing T1 lesions or new or enlarging T2-weighted lesions observed on brain MRI at Weeks 4, 8, and 12 will use a logistic regression model similar as described for the primary endpoint. A hypothetical strategy will also be used as defined in Section 5.3.2.

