3. OBJECTIVES AND ENDPOINTS

This study will evaluate the efficacy, safety, and pharmacokinetics of fenebrutinib compared with placebo in participants with RMS. Specific objectives and corresponding endpoints for the study are outlined in [Table 4](#) and [Table 5](#).

Table 4 Primary and Secondary Objectives and Corresponding Estimands

Primary Objective	Estimand Definition

 To evaluate the efficacy of fenebrutinib compared with placebo on the total number of new gadolinium-enhancing T1 MRI lesions 	
 Population: all randomized patients Endpoint: Total number of new gadolinium-enhancing T1 lesions observed on MRI scans of the brain at Weeks 4, 8, and 12 Treatment: 
 200 mg BID oral fenebrutinib placebo Intercurrent events and handling strategy: 
 Withdrawal from treatment: hypothetical strategy Initiation of another MS therapy: not allowed while on study. In case of such intercurrent event: hypothetical strategy Population level summary: rate ratio from Negative Binomial model
Secondary Objectives	Estimand Definition

 To evaluate the effect of fenebrutinib on MRI lesions 	
 Population: all randomized patients Endpoint: 
 Total number of new or enlarging T2-weighted lesions observed on brain MRI at Weeks 4, 8, and 12 Proportion of participants free from any new gadolinium-enhancing T1 lesions and new or enlarging T2-weighted lesions observed on brain MRI at Weeks 4, 8, and 12 Treatment: 
 200 mg BID oral fenebrutinib placebo Intercurrent events and handling strategy: 
 Withdrawal from treatment: hypothetical strategy (see Section 9.4.3) Initiation of another MS therapy: not allowed while on study. In case of such intercurrent event: hypothetical strategy Population level summary: 
 For Endpoint (1): rate ratio from Negative Binomial model For Endpoint (2): odds ratio from logistic regression model

BID = twice a day; MRI = magnetic resonance imaging

Table 5 Other Secondary and Exploratory Objectives and Endpoints

Secondary Objectives	Corresponding Endpoints

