9.4.2 Primary Endpoint(s)

The primary endpoint is the total number of new T1 Gd+ lesions observed on MRI scans of the brain at Weeks 4, 8, and 12. The total number of *new* T1 Gd-enhanced lesions is

the sum of the individual number of *new* T1 Gd-enhanced lesions at Weeks 4, 8, and 12.

The primary estimand follows a hypothetical strategy and estimates the treatment effect of fenebrutinib versus placebo had the patient not experienced an intercurrent event on the basis of the following attributes:

- Population: all randomized participants.
- Variable: total number of new T1 Gd+ lesions as described in Section 8.1.1
- Intercurrent events:
 - Withdrawal from treatment: Data after participants withdrawn from treatment will be censored, following a hypothetical strategy.
 - Initiation of another MS therapy: Initiation of another MS therapy is not allowed while on study. In case of such intercurrent event, patient will be considered as censored after initiation of another MS therapy, following a hypothetical strategy.
- Population-level-summary estimator: The total number of new T1 Gd+ lesions of primary analysis will be compared between the fenebrutinib and placebo using the negative binomial model, adjusting for stratification factor(s) (Section 6.3.1). In case of early discontinuations, different number of scans among participants may be observed. Log-transformed number of scans will be included in the negative binomial model as an “offset” variable to account for different number of scans. The rate ratio and its two-sided 95% confidence intervals will be presented along with the p-value.
- Handling of missing data:
 - Withdrawal from study: no imputation will be conducted for missing data. The negative binomial model with including number of scans as an “offset” variable accounts for different number of scans.

If the model fails to converge due to high number of zero T1 Gd+ lesion counts, a logistic regression model will be performed on the status of new T1 Gd+ lesion post-baseline (present or not) adjusted for the same stratification factor(s). The odds ratio and its two-sided 95% confidence intervals will be presented along with the p-value. A hypothetical strategy will be used:

- Data after participants withdrawn from treatment will be censored.
- For the intercurrent event of withdrawal from treatment:
 - Those withdrawn because of lack of efficacy or death and having no T1 Gd+ lesions are considered as having T1 lesions

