9.4.3 Secondary Endpoints

The estimands for the secondary endpoint of total number of new or enlarging T2 lesions, as defined in Section 3 (Table 3), will follow the same hypothetical strategy and have the same attributes as for the primary endpoint. Number of new or enlarging T2 lesions and proportion of participants with new or enlarging T2 lesions at each scheduled visit will also be summarized by treatment groups.

The secondary endpoint of proportion of participants free from any new gadolinium-enhancing T1 lesions and new or enlarging T2-weighted lesions observed on brain MRI at Weeks 4, 8, and 12 will use a logistic regression model similar as described for the primary endpoint. A hypothetical strategy will also be used:

- Data after participants withdrawn from treatment will be censored.
- For the intercurrent event of withdrawal from treatment:
 - Those withdrawn because of lack of efficacy or death and having no T1 Gd+ lesions or new or enlarging T2 lesions are considered as not free from lesions.
 - Otherwise, no imputation will be conducted.

Safety will be assessed through summaries of exposure to study treatment, adverse events, changes in laboratory test results, and changes in vital signs.

All verbatim adverse event terms will be mapped to Medical Dictionary for Regulatory Activities thesaurus terms, and adverse event severity will be graded according to the most current version of NCI CTCAE. All adverse events, serious adverse events, adverse events leading to death, adverse events of special interest, and adverse events leading to study treatment discontinuation that occur on or after the first dose of study treatment (i.e., treatment-emergent adverse events) will be summarized by mapped term, appropriate thesaurus level, and severity grade. For events of varying severity, the highest grade will be used in the summaries. Deaths and cause of death will be summarized.

Relevant laboratory and vital sign (pulse rate, respiratory rate, blood pressure, pulse oximetry, and temperature) will be displayed by time, with grades identified where appropriate. Additionally, a shift table of selected laboratory tests will be used to summarize the baseline and maximum postbaseline severity grade. Changes in vital signs will be summarized.

Proportion of participants with suicidal ideation or behavior, as assessed by Columbia-Suicide Severity Rating Scale, will be summarized.

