## 1. INTRODUCTION

Study GN43271 is a Phase II study to assess the efficacy, safety, and pharmacokinetics of fenebrutinib, a highly selective, orally administered, adenosine triphosphate (ATP)-competitive, reversible inhibitor of Bruton’s tyrosine kinase (BTK), compared with placebo in participants with relapsing multiple sclerosis (RMS). This Statistical Analysis Plan (SAP) provides details of the planned analyses and statistical method for the study and supersedes analysis details specified in the protocol.

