**Table 1 Primary and Secondary Objectives and Corresponding Estimands**

	
 
• Treatment: 
 
– 200 mg BID oral fenebrutinib
 
– placebo
 
 
 
 <hr/> 
 
• Intercurrent events and handling strategy: 
 
– Withdrawal from treatment: hypothetical strategy (see Section 5.4.1)
 
– Initiation of another MS therapy: not allowed while on study. In case of such intercurrent event: hypothetical strategy
 
 
 
 <hr/> 
 
• Population level summary: 
 
– For Endpoint (1): rate ratio from Negative Binomial model
 
– For Endpoint (2): odds ratio from logistic regression model
 
 
 

--	---

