#### **5.3.2 Main Analytical Approach for Primary Endpoint(s)**

The primary estimand follows a hypothetical strategy and estimates the treatment effect of fenebrutinib versus placebo had the patient not experienced a protocol defined intercurrent event on the basis of the following attributes:

- Population: all randomized participants.
- Variable: total number of new T1 Gd+ lesions as described in Section [5.3.1](#)
- Treatment:
  - 200 mg BID oral fenebrutinib
  - placebo
- Intercurrent events:
  - Withdrawal from treatment: Data after participants withdrawn from treatment will be censored, following a hypothetical strategy.
  - Initiation of another MS therapy: Initiation of another MS therapy is not allowed while on study. In case of such intercurrent event, patient will be considered as censored after initiation of another MS therapy, following a hypothetical strategy.
- Population-level-summary estimator: The total number of new T1 Gd+ lesions of primary analysis will be compared between the fenebrutinib and placebo using the negative binomial model, adjusting for stratification factor(s) (presence or absence of T1 Gd+ lesions on the screening MRI). In case of early discontinuations, different number of scans among participants may be observed. Log-transformed number of

scans will be included in the negative binomial model as an “offset” variable to account for different number of scans. The rate ratio and its two-sided 95% confidence intervals will be presented along with the p-value.

- Handling of missing data:
  - Withdrawal from study: no imputation will be conducted for missing data. The negative binomial model with number of scans as an “offset” variable accounts for different number of scans.

If the model fails to converge due to high number of zero T1 Gd+ lesion counts, a logistic regression model will be performed on the status of new T1 Gd+ lesion post-baseline (present or not) adjusted for the same stratification factor(s). The odds ratio and its two-sided 95% confidence intervals will be presented along with the p-value. A hypothetical strategy will be used as defined above.

Number of new T1 Gd+ lesions and proportion of participants with new T1 Gd+ lesions at each scheduled visit will be summarized by treatment groups.

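### Does the SAP's missing rule for withdrawals due to lack of efficacy or death put the lesion-free endpoint at risk?

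*SAP*

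**What the plan says.** In Protocol Table 4, the entry for the secondary MRI endpoints reads "Withdrawal from treatment: hypothetical strategy (see Section 9.4.3". Protocol 9.4.3 then censors data after withdrawal from treatment and adds one exception: participants who withdrew for lack of efficacy or death, "having no T1 Gd+ lesions or new or enlarging T2 lesions are considered as not free from lesions". Nothing else is imputed. Protocol 9.4.2 has the matching exception for the logistic model that replaces the primary analysis if the negative binomial model does not converge: "Those withdrawn because of lack of efficacy or death and having no T1 Gd+ lesions are considered as having T1 lesions".

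SAP Table 1 carries the same pointer, redirected: "Withdrawal from treatment: hypothetical strategy (see Section 5.4.1". Under that heading, SAP 5.4.1.2 says "A hypothetical strategy will also be used as defined in Section 5.3.2". SAP 5.3.2 estimates the effect "had the patient not experienced a protocol defined intercurrent event", censors after withdrawal or another MS therapy, and states that "no imputation will be conducted for missing data". Neither section contains the lack-of-efficacy/death exception. SAP Section 1 says that the SAP "supersedes analysis details specified in the protocol".

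**The concern.** The SAP was written from the protocol version that contains the exception. Its Table 1 keeps the cross-reference, but the exception is not at the place it points to, and the SAP lists no section for changes from the protocol. A reader cannot tell a deliberate removal from an oversight.

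The SAP also leaves a related gap. In the negative binomial model, unequal numbers of scans are handled by the offset. A logistic model of lesion-free status has no offset, and the SAP does not say whether someone censored after one or two clean scans is lesion-free or not evaluable.

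The endpoint is listed among the key secondary endpoints in SAP 5.4.1, and Protocol 9 foresees significance testing of secondary endpoints. With only 34 placebo participants, one person's classification can visibly move the odds ratio.

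**Working it through.** **Inputs.** SAP Section 3 gives 0.7 new T1 lesions per scan on placebo, a 60% reduction (0.28 per scan on fenebrutinib), allocation 34:68 and about 3% dropout. There are three scans, so the means are 2.1 and 0.84. Neither document states the dispersion k or a T2 lesion rate. I assume k = 1 (range 0.5 to 2) and let T1 rates stand in for the combined endpoint.

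**The plan's own figure.** Placebo n = (1.960 + 1.282)² × [(1/2.1 + k) + (1/0.84 + k)/2] / (ln 0.4)². At k = 1 this is 10.51 × 2.571 / 0.840 = 32.2, so 33 placebo and 99 in total. Adding 3% (99 × 1.03) gives 102. The stated size is consistent with k = 1.

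**True odds ratio.** The probability of no lesion is (1 + k × mean)^(−1/k).
- Three scans, k = 1: placebo 1/3.1 = 0.323; fenebrutinib 1/1.84 = 0.543. OR = 2.50.
- One scan, k = 1: placebo 1/1.7 = 0.588; fenebrutinib 1/1.28 = 0.781.

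**How many people are affected.** Clean leavers expected at 3%, leaving after one scan: 0.03 × (34 × 0.588 + 68 × 0.781) = 2.2. Only those who left for lack of efficacy or death are classified differently by the two documents.

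**Average OR, 3% dropout in each arm after one scan, k = 1.** Let q be the share of leavers in both arms with one of the two reasons. The lesion-free proportion under the protocol is 0.97 × P(3 scans) + 0.03 × (1 − q) × P(1 scan).

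| Rule | Placebo | Fenebrutinib | OR |
|---|---|---|---|
| SAP, status on observed scans (q = 0) | 0.3306 | 0.5506 | 2.48 |
| Protocol, q = 0.25 | 0.3261 | 0.5448 | 2.47 |
| Protocol, q = 1 | 0.3129 | 0.5272 | 2.45 |
| SAP, clean leavers not evaluable | – | – | 2.51 |
| SAP, all incomplete participants excluded | – | – | 2.50 |

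Across these readings the range is 3.09 to 3.16 at k = 0.5 (true 3.15) and 1.96 to 2.02 at k = 2 (true 2.01).

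**Unequal reasons.** With 3% dropout per arm and all lack-of-efficacy or death withdrawals in one arm, the protocol rule gives 2.26 (fenebrutinib only) or 2.69 (placebo only). At the expected counts of 37/68 versus 11/34, the standard error of the log OR is √(1/37 + 1/31 + 1/11 + 1/23) = 0.44. The distance from 2.48 is ln(2.69/2.48)/0.44 = 0.18 or ln(2.48/2.26)/0.44 = 0.21 standard errors.

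**Extreme case.** If the whole 3% of 102 (about 3 people, 9% of 34) left the placebo arm after one scan, all for these reasons, the protocol rule gives 2.87 and the SAP on observed scans 2.25. That is ln(2.87/2.25)/0.44 = 0.55 standard errors.

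**One participant, unadjusted Wald test.** The base of 37/68 versus 11/34 gives OR 2.50, p = 0.038. Moving one placebo participant to not free gives 37/68 versus 10/34, OR 2.86, p = 0.019. Moving one fenebrutinib participant gives 36/68 versus 11/34, OR 2.35, p = 0.052.

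**Simulated trials of 34/68.** At 3% dropout per arm, with a quarter of leavers in both arms having these reasons, the two rules disagreed on nominal p < 0.05 in 2.4% to 3.4% of trials (k from 0.5 to 2, leaving after one or two scans).

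**The case for a change.** The strongest case for acting is that the precedence clause says which document governs but not whether the omission was meant, and that it does not complete the SAP's rule. Both points are correct. The protocol presents its statistical section as a summary that the SAP will detail; here the SAP has less detail. The reason for stopping treatment is already recorded on the eCRF, so writing the rule down would cost little. In a small trial a single reclassification can carry a result across 0.05, as shown above. With 10% dropout in one arm and 3% in the other, the choice for incomplete clean participants also matters more: status on observed scans gives 2.28 (10% on placebo) or 2.65 (10% on fenebrutinib) against a true 2.50, while excluding incomplete participants gives 2.50 when dropout is unrelated to lesions.

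This supports a documentation note and does not show a defect in the planned analysis. The protocol exception treats withdrawal as failure, which is a composite rule under a hypothetical label. Restoring it would bring back a mismatch that the SAP avoids, or would mean relabelling the estimand in both documents. Choosing between the two strategies is a fair trade-off. The p-value shifts arise because the expected result lies close to 0.05, where any recoding of one person can tip it. The shares of withdrawals by reason are assumptions with no source in the documents. Few such withdrawals are likely in 12 weeks: Protocol 6.8.1.3 says a relapse alone should not end treatment, and treating investigators do not see post-randomization scans unless a safety concern arises.

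**Conclusion.** The textual difference is real: the SAP drops a protocol rule without saying so, and the Table 1 pointer leads to no specific instruction. It does not leave the choice of rule open after unblinding, because the SAP takes precedence and is to be final before then. Followed as written, the SAP gives a sound analysis at the planned dropout: 2.48 to 2.51 on its possible readings, against a true 2.50 and a protocol-rule value of 2.45 to 2.47. The unstated handling of participants with fewer than three scans, all clean, is ordinary detail for the analysis programming.

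This rests on dispersion near 1, T1 rates standing in for the combined endpoint, dropout unrelated to lesions, and dropout near 3% with similar reasons in both arms. With such withdrawals in one arm only, the gap is about 0.2 standard errors; in the extreme placebo-only case it is about 0.55. The primary negative binomial analysis is not affected; only its logistic fallback shares the omission. No change to the plan is needed.

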### **5.4.2 Supportive Secondary Endpoint(s)**

The secondary safety endpoints are:

- Incidence and severity of adverse events
- Change from baseline in vital signs
- Change from baseline in targeted clinical laboratory test results (Hematology, chemistry, hepatic synthetic function tests, lipids, and Igs)
- Proportion of participants with suicidal ideation or behavior, as assessed by Columbia-Suicide Severity Rating Scale

The secondary PK endpoint is:

- Plasma concentration of fenebrutinib at specified timepoints

#### **5.4.2.1 Secondary safety endpoints**

Safety will be assessed through summaries of exposure to study treatment, adverse events, changes in laboratory test results, changes in vital signs, and by the proportion of patients with suicidal ideation or behavior as assessed by Columbia-Suicide Severity Rating Scale (C-SSRS) scores.

All verbatim adverse event terms will be mapped to Medical Dictionary for Regulatory Activities (MedDRA) thesaurus terms, and adverse event severity will be graded according to the most current version of National Cancer Institute Common Terminology Criteria for Adverse Events (NCI CTCAE). All adverse events, serious adverse events, adverse events leading to death, adverse events of special interest, and adverse events leading to study treatment discontinuation that occur on or after the first dose of study treatment (i.e., treatment-emergent adverse events) will be summarized by mapped term, appropriate thesaurus level, and severity grade. For events of varying severity, the highest grade will be used in the summaries. Deaths and cause of death will be summarized.

Relevant laboratory and vital signs will be displayed by time and grade identified when associated with an adverse event. Additionally, a shift table of selected laboratory tests will be used to summarize the baseline and maximum postbaseline severity grade. Changes in vital signs will be summarized.

Proportion of participants with suicidal ideation or behavior, as assessed by Columbia-Suicide Severity Rating Scale, will be summarized.

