8.2.4 Clinical Safety Laboratory Assessments

See [Appendix 2](#) for the list of clinical laboratory tests to be performed and to the schedule of activities (see Section [1.3](#)) for the timing and frequency.

The investigator must review the laboratory report, document this review, and record any clinically relevant changes occurring during the study in the Adverse Event CRF. The laboratory reports must be filed with the source documents. Clinically significant abnormal laboratory findings are those that are not associated with the underlying disease, unless judged by the investigator to be more severe than expected for the participant's condition. A laboratory test result must be reported as an adverse event if it meets any of the following criteria:

- Is accompanied by clinical symptoms

- Results in a change in study treatment (e.g., dosage modification, treatment interruption, or treatment discontinuation)
- Results in a medical intervention (e.g., potassium supplementation for hypokalemia) or a change in concomitant therapy
- Is clinically significant in the investigator's judgment
- ALT or AST > 3 × ULN unless attributed to a specific clinical diagnosis that is to be reported as the primary adverse event term (*see Section 8.3.1 for more information on AE categories*).

Medical and scientific judgment should be exercised in deciding whether an isolated laboratory abnormality should be classified as an adverse event.

All laboratory tests with values considered clinically significantly abnormal during participation in the study or within 4 weeks of the final dose of study treatment should be repeated until the values return to normal or baseline or are *considered to be stable and* no longer considered clinically significant by the investigator. If such values do not return to normal or baseline within a period of time judged reasonable by the investigator, the etiology should be identified and the Sponsor notified.

All protocol-required laboratory assessments, as defined in [Appendix 2](#), must be conducted in accordance with the laboratory manual and the schedule of activities.

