A persistent adverse event is one that extends continuously, without resolution, between patient evaluation timepoints. Such events should only be recorded once on the Adverse Event eCRF. The initial severity (intensity or grade) of the event will be recorded at the time the event is first reported. If a persistent adverse event becomes more severe, the most extreme severity should also be recorded on the Adverse Event eCRF. If the event becomes serious, it should be reported to the Sponsor immediately (i.e., no more than 24 hours after the investigator becomes aware that the event became serious; see Section [A3–5](#) for reporting instructions). The Adverse Event eCRF should be updated by changing the event from "non-serious" to "serious," providing the date that the event became serious, and completing all data fields related to serious adverse events.

A recurrent adverse event is one that resolves between patient evaluation timepoints and subsequently recurs. Each recurrence of an adverse event should be recorded as a separate event on the Adverse Event eCRF.

A3–7.4 ABNORMAL LABORATORY VALUES

Not every abnormal laboratory value qualifies as an adverse event. A laboratory value abnormality that is associated with the underlying disease should not be reported as an adverse event unless judged by the investigator to be more severe than expected.

A laboratory value abnormality that is not associated with the underlying disease must be reported as an adverse event if it meets any of the following criteria:

- Is accompanied by clinical symptoms
- Results in a change in study treatment (e.g., dose modification, treatment interruption, or treatment discontinuation)
- Results in a medical intervention (e.g., potassium supplementation for hypokalemia) or a change in concomitant therapy
- Is clinically significant in the investigator's judgment
- ALT or AST $> 3 \times$ upper limit of normal (ULN) unless this is attributed to a specific clinical diagnosis that is to be reported as the primary adverse event term

It is the investigator's responsibility to review all laboratory findings. Medical and scientific judgment should be exercised in deciding whether an isolated laboratory abnormality should be classified as an adverse event (except for ALT/AST $> 3 \times$ ULN, which must always be reported as an adverse event in this protocol).

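### SAP 5.4.2.1 shows a laboratory grade in the by-time display only when the value is tied to an adverse event, leaving asymptomatic, unmanaged abnormalities ungraded unless the test is in an unnamed shift-table list

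*SAP*

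**What the plan says.** SAP 5.4.2.1 gives this rule for the by-time safety display: "Relevant laboratory and vital signs will be displayed by time and grade identified when associated with an adverse event". Its next sentence adds a second, separate output: "a shift table of selected laboratory tests will be used to summarize the baseline and maximum postbaseline severity grade". That table carries no adverse-event condition, but neither the SAP nor the protocol names the tests in it.

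Protocol 9.4.3 describes the same display differently. Laboratory values and vital signs "will be displayed by time, with grades identified where appropriate". SAP section 1 says that the SAP "supersedes analysis details specified in the protocol", so the narrower SAP rule governs.

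The laboratory secondary endpoint in SAP 5.4.2 is change from baseline in five groups of tests: hematology, chemistry, hepatic synthetic function, lipids and immunoglobulins.

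On when a laboratory result becomes an adverse event, protocol Appendix 3 (A3-7.4) starts from "Not every abnormal laboratory value qualifies as an adverse event". Protocol 8.2.4 adds: "Medical and scientific judgment should be exercised in deciding whether an isolated laboratory abnormality should be classified as an adverse event". The exception triggered by the value alone is ALT or AST above 3 × ULN, "which must always be reported as an adverse event in this protocol" (A3-7.4).

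**The concern.** A laboratory grade can be computed from the value and its reference range, without anyone deciding whether the finding deserves a report. Tying the grade to an adverse event gives up that advantage in the by-time display. Two participants with the same result at the same visit can then be shown differently because one investigator recorded an event and the other did not.

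This matters most for mild to moderate findings that cause no symptoms and prompt no action. Protocol A6-1.6 lists cytopenias as an observed finding with this drug, so a complete count of low-grade neutropenia by visit is something a reader of the safety report would want. If the grade column partly mirrors the adverse-event table, it adds less independent information than it appears to.

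**Working it through.** No arithmetic applies. The SAP states a reporting rule, and neither document gives a figure for it that could be reproduced. The check is to ask, for each kind of abnormal result, whether the documents force an adverse-event record and therefore a grade in the by-time display.

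Mandatory triggers in protocol 8.2.4 and A3-7.4 are: symptoms; a change in study treatment, including interruption; an intervention or a change in concomitant therapy; and ALT or AST above 3 × ULN. The remaining criterion is the investigator's view that the result is clinically significant.

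| Abnormal result | Is an adverse-event record forced? | Grade in by-time display |
|---|---|---|
| ALT or AST above 3 × ULN | Yes, by the value (A3-7.4, A3-7.6) | Yes |
| Any result with symptoms, a treatment change or an intervention | Yes (8.2.4, A3-7.4) | Yes |
| First Grade 2 thrombocytopenia or Grade 3 neutropenia | Yes where the hold in Table A6-1 is applied, since a hold is an interruption | Yes |
| Grade 4 neutropenia; Grade 3 or 4 thrombocytopenia | Yes, section 7.1 requires discontinuation | Yes |
| Grade 2 neutropenia without symptoms or action | No; Table A6-1 maintains dosing, so it rests on judgment | Depends on the site |
| Isolated bilirubin or lipase elevation without symptoms or action | No; it rests on judgment | Depends on the site |

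For every row, the shift table would show the grade if the test is among those selected. Which tests those are is not stated.

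Two further provisions show that adverse-event records cannot supply a grade at each visit even when a report exists. Under A3-7.4 the same abnormality seen at successive visits is recorded once. Under A3-7.3 a persistent event carries its initial severity and its most extreme severity. The SAP also gives no rule for matching a laboratory record to an adverse event.

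Immunoglobulins are in the targeted list but are blinded until the primary database lock (SAP 1.2.1). A low value could therefore hardly prompt a report during the double-blind phase. Whether these results have a grade at all is not stated in the documents.

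The gap is thus the intersection of two conditions: the abnormality is asymptomatic and unmanaged, and its test lies outside the shift-table selection.

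**The case against.** The strongest reply is that little is lost. The endpoint is change from baseline, not grade. SAP 5.4.2.1 summarizes changes in laboratory results and displays values by time with no adverse-event condition on either. The shift table, graded from values, is the main summary of laboratory toxicity, and limiting it to a selection is the protocol's own wording too. The serious hematologic and hepatic findings are pulled in by the mandatory triggers. All of this stands and sets the scope of the point.

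Several stronger readings are tempting and should be resisted:

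- A reader might infer that, apart from ALT and AST, reporting is entirely at the investigator's discretion. Protocol 8.2.4 and A3-7.4 contradict that, as the mandatory triggers show.
- A reader might infer that the laboratory secondary endpoint itself now depends on adverse-event reporting. It does not; the condition attaches to the grade only.
- A reader might infer that cytopenias or bilirubin are left out of the shift table. The list is open, which is not evidence of omission.
- A reader might want a count of missed grades. That needs a prevalence and a reporting rate for asymptomatic abnormalities, and the documents give neither. The one related figure, 1% to 10% of participants on 200 mg BID with Grade 2 or higher transaminase elevations (A6-1.1), concerns the class for which reporting is mandatory.
- A reader might infer bias between arms. Investigators are blinded to treatment, and nothing in the documents shows reporting to differ by arm.

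What the reply does not remove is the rule itself. The SAP chose a condition that the protocol did not contain, and it offers no guarantee that the shift table fills the gap.

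**Conclusion.** The point holds in limited form. For tests outside the unnamed shift-table selection, asymptomatic and unmanaged abnormalities receive a grade in the by-time display only if an investigator chose to report them. Grade 2 neutropenia, isolated bilirubin and isolated lipase are examples of the type of result exposed; they are not known omissions.

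The conclusion rests on two assumptions: that the SAP sentence is applied as written, and that the shift-table selection does not already include every gradable hematology and chemistry test. If it does include them, the worst grade is recovered for those tests and only the visit-by-visit grades remain incomplete.

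The size cannot be stated from the documents. The consequence is confined to a descriptive safety display; no efficacy estimate, test, error rate or sample size is touched. It is still worth correcting, because the stated method is weaker than a cheap alternative and departs from the protocol.

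**What to change.** In SAP 5.4.2.1, delete the adverse-event condition for laboratory values. State instead that every gradable targeted laboratory result is graded from its value and reference range using CTCAE v5.0, whether or not an adverse event was reported. Naming the version aligns the SAP, which refers only to the most current one, with protocol A3-3.2. Investigator grades of adverse events stay in the adverse-event tables.

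Before unblinding, set the shift-table tests to be at least the gradable hematology and chemistry tests, and list them.

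The cost is slightly longer tables and standard programming. One limit should be acknowledged in the text. At Weeks 2, 6 and 10 the limited chemistry panel may be run locally, and Table 1 footnote b routes those results to the adverse-event form when applicable. Grades can be derived only for results that reach the database.
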